7.2 Exclusion Criteria

To be eligible for enrollment into this study, each subject must not meet any of the following criteria at screening (unless otherwise specified):

1. Weight gain or weight loss of greater than 5 kg, use of a supervised fast or very low-

calorie diet within the past 3 months;

2. Treatment with phentermine, topiramate, lorcaserin, naltrexone HCl/bupropion HCl, any over-the-counter (OTC) or prescription or herbal agents and dietary supplements, teas or tinctures used with the intention to lose body weight within 3 months of screening;
3. Any stimulants used for treatment of attention-deficit/hyperactivity disorder (ADHD) within 3 months of screening;
4. Condition or disease interfering with metabolism, such as untreated hypothyroidism, Cushing's syndrome;
5. Pulmonary disorders (other than asthma not requiring continuous medication or sleep apnea-related disorders);
6. Type 1 diabetes or any medical treatment with insulin, sulfonylureas (SFUs), glucagon-like peptide-1 (GLP-1) agonists, sodium glucose transporter (SGLT-1) inhibitors, and SGLT-2 inhibitors;
7. Congenital heart disease;
8. Clinically significant arrhythmia or electrocardiogram (ECG) abnormality;
9. Screening laboratory values as specified (tests may be repeated per investigator's discretion):

a. Bicarbonate	< LLN
b. AST and ALT	> 3 x ULN
c. HbA1c	≥ 8.0 %
d. Fasting glucose	≥ 270 mg/dL
e. Triglyceride	≥ 400 mg/dL
f. Creatinine clearance	< 60 mL/minute (Schwartz Formula) ⁷ (see Appendix 7: Formulas for Estimating Creatinine Clearance)
g. TSH	> 1.5 ULN
10. Clinically significant hepatic or renal disease;
11. Clinically significant thyroid dysfunction as evidenced by signs or symptoms of hypothyroidism, a thyroid stimulating hormone (TSH) > 1.5 x ULN, or use of thyroid hormone treatment that has not been stable for at least 3 months;
12. Systolic blood pressure > 140 mmHg, diastolic blood pressure > 90 mmHg or concurrent antihypertensive medication that has not been stable for 3 months;
13. Any history of bipolar disorder or psychosis, greater than one lifetime episode of major depressive disorder, current depression of moderate or greater severity (PHQ-9 score of 10 or more), presence or history of suicidal behavior or ideation with some intent to act on it; tricyclic antidepressants, monoamine oxidase inhibitors (MAOIs), lithium, levodopa, and dopamine receptor agonists; or allowed antidepressant use that has not been stable for at least 3 months;
14. Use of chronic systemic glucocorticoid therapy (i.e. glucocorticoids, anabolic steroids) or any other steroid hormone therapy other than oral contraceptives, that has not been stable for at least 3 months;

15. Pregnancy or breastfeeding;
16. Any history of eating disorders (e.g. bulimia; binge eating disorder; anorexia);
17. Any history of laxative abuse;
18. History of glaucoma, use of carbonic anhydrase inhibitors, history of increased intraocular pressure or any past or present use of medications to treat increased intraocular pressure;
19. Prior bariatric surgery;
20. Any history of nephrolithiasis;
21. Any history of epilepsy, or requirement for anticonvulsants used for treatment of seizure disorder, including barbiturates, benzodiazepines, gamma-aminobutyric acid (GABA) analogues, hydantoins, phenyltriazines, succinimides, and other agents (valproic acid and its derivatives, carbamazepine and its derivatives, zonisamide, and felbamate);
22. Positive urine drug screen;
23. Current smoker or smoking cessation within 3 months of screening;
24. Obesity of a known genetic or endocrine origin, such as Prader-Willi Syndrome;
25. Known allergy or hypersensitivity to phentermine or topiramate or history of anaphylaxis to any drug;
26. Use of any investigational medication or device for any indication or participation in a clinical study within 30 days prior to screening; or
27. Other clinically significant medical or psychiatric condition or laboratory abnormality that may increase the risk associated with trial participation or investigational product administration or may interfere with the interpretation of trial results and, in the judgment of the investigator, would make the subject inappropriate for entry into this trial.

7.3 Subject Withdrawal

Subjects are free to withdraw from the clinical trial or discontinue treatment at any time for any reason.

The sponsor reserves the right to discontinue this trial at any time (see Section 13.0 on clinical trial discontinuation criteria).

Subject participation in this clinical trial may be discontinued for any of the following reasons:

- Occurrence of any medical condition or circumstance that exposes the subject to substantial risk and/or does not allow the subject to adhere to the requirements of the protocol;
- Any serious adverse event (SAE), clinically significant adverse event (AE), severe laboratory abnormality, intercurrent illness, or other medical condition that indicates to the Investigator that continued participation is not in the best interest of the subject;
- Subject's (or a parent's or legal guardian's) decision to withdraw;
- Requires other medical treatment that is excluded by the protocol (see Section 8.5);

- Subject failure to comply with protocol requirements or study related procedures; or
- Termination of the clinical trial by the sponsor, FDA, or other regulatory authorities.

Withdrawn subjects will not be replaced.

Subjects discontinued from treatment should be encouraged to remain in the trial off-treatment and to continue study visits at the scheduled intervals. Subjects who withdraw completely from the trial at any point should complete the end of study (Visit 16, Week 56) procedures. The date of last dose should be recorded.

Every effort should be made to document subject outcome. For subjects who elect to withdraw from the trial without continuing study visits, the investigator should inquire about the reason for withdrawal, request that the subject return all unused investigational product(s), request that the subject return for a final visit (Section 9.1.4) and follow-up with the subject regarding any unresolved adverse events.

At about the 56-week time point, withdrawn subjects who have not continued study visits should be asked to return to the site to obtain weight and height measurements at a minimum and, if possible, all the other tests and procedures (except physical examination and ECG) required for end of study visit.

If a subject withdraws from the trial and also withdraws consent for disclosure of future information, no further evaluations will be performed and no additional data will be collected. The sponsor may retain and continue to use any data collected before such withdrawal of consent.

8.0 TREATMENT OF SUBJECTS

8.1 Study Treatment

Eligible subjects will receive 56 weeks of treatment with either VI-0521, or matching placebo for daily use.

8.2 Allocation to Treatment

Written informed consent will be obtained prior to the performance of any study-related procedures. Eligible subjects will be randomly assigned in a 1:1:2 ratio to placebo, mid-dose (PHEN/TPM 7.5 mg/46 mg) or top-dose (PHEN/TPM 15 mg/92 mg) of VI-0521. Randomization will be stratified by gender and age (12-14 vs 15-16 years old), and will be implemented using an Interactive Web Response System (IWRS). The sponsor, the subjects, and the study site will be blinded as to subject randomization.

When a subject qualifies for randomization, site personnel will log into the IWRS to obtain a specific titration blister card or bottle number to dispense to the study subject. The subject will return the study drug at every clinic visit for drug accountability and will be dispensed with a new blister card/bottle for the next treatment period.

8.3 Breaking the Blind

Study drug must not be unblinded during the study unless it is considered absolutely necessary

by the investigator for the management of an adverse event or other medical emergency. Under such conditions, investigators will first contact the medical monitor when deciding to unblind a subject and if unblinding is deemed medically necessary the identity of the study treatment may be obtained via the IWRS. Any subject whose treatment assignment has been unblinded must be withdrawn from the study.

Investigators are also required to ensure that any potential SAEs are reported according to the requirements outlined in Section 11.1.5 and provide a written report to VIVUS or designee within 7 days to document the reason for unblinding.

8.4 Drug Supply

Clinical supplies will be manufactured for VIVUS by in accordance with current Good Manufacturing Practices (cGMP). All clinical supplies will be labeled with information required by national regulations.

8.4.1 Formulation and Packaging

Sufficient quantities of VI-0521, phentermine and topiramate capsules will be supplied by the sponsor in blister cards and bottles and shipped to a designee at the study site. All clinical supplies will be labeled with information required by national and/or international regulations. Study drug will be packaged into 2 types of kits; titration kits (blister cards) for use during the first 4 weeks of study treatment and the titration period during study Weeks 13-16, and treatment kits (bottles), for use once subjects have been titrated to their assigned dose.

Each titration kit contains 1 blister card for use during Weeks 1 through 4 of titration, with each card containing 4 columns of 8 capsules each. Each column on the blister card will be labeled with the week number (1 through 4) and will contain capsules with the dose specified for that week of treatment, as outlined in Table 1. Titration kits will consist of blister cards labeled with the study number, a unique kit number, storage instructions, and spaces for the subject number and initials. Treatment kits will consist of bottles, each containing 35 capsules of study medication at the treatment dosages shown in Table 1. Each kit will contain a single bottle labeled with the study number, a unique kit number, storage instruction, and spaces for the subject number and initials.

Table 1: VI-0521 Dosage Strengths by Titration Week for Each Treatment Group

Group	Treatment Dosage for Phentermine/Topiramate (mg)	Titration Dose for Phentermine/Topiramate (mg)			
		Weeks 1-2	Weeks 3-4	Weeks 13-14	Weeks 15-16
Placebo	0/0	0/0	0/0	0/0	0/0
VI-0521 Mid	7.5/46	3.75/23	7.5/46	7.5/46	7.5/46
VI-0521 Top	15/92	3.75/23	7.5/46	11.25/69	15/92

8.4.2 Preparation and Dispensing

Clinical supplies provided by the sponsor are to be dispensed only by or under the direct supervision of qualified investigators to subjects meeting the criteria for study entry and in accordance with this protocol. Randomization scheme will be followed by site staff for assignment of specific bottle to study subjects. No other preparation of clinical supplies is required of the study staff.

8.4.3 Administration

Subjects will be instructed to take 1 capsule of study drug every morning with or without food, and with water. Subjects should stay hydrated by drinking plenty of water while in the study. Subjects will be reminded not to take study drug to school or work. Capsules are not to be broken or split apart in any manner.

When dispensing titration kits, investigators should ensure that subjects understand that each blister card contains a 4-week supply of medication, and that the capsules must be taken in a specific order (i.e. Week 1 before Week 2, and Week 3 before Week 4).

When dispensing study drug bottles, investigators should ensure that subjects understand that each bottle contains a 4-week supply of study drug, and that the capsules must be taken for the treatment period that the bottle is dispensed for. Instruction should also be provided that each bottle contains extra capsules that should only be taken should the next study visit be scheduled beyond 4 weeks after the previous visit. Investigators will also instruct subjects to return all study drug (blister card and the bottle, even if empty) to the site at each study visit.

8.4.4 Dose Reduction and/or Interruption During Trial Participation

Dose reduction is an option for subjects who experience adverse events that are sufficiently severe to cause the subject to consider discontinuation or to cause the investigator concern about the subject's ability to continue in the study.

It should be recognized that caloric restriction resulting in rapid weight loss (independent of any specific drug mechanisms) carries the potential to negatively affect growth. Due to the potential of the study drug to cause significant weight loss which may affect growth in adolescents, investigators should actively monitor the subject's rate of weight loss and growth (using height and weight), and implement a down-titration of study drug should rates of weight loss in a given subject exceed rates that are deemed safe. For subjects with baseline BMI 95-98th percentile, reduce study drug dosage when BMI is < 85th percentile or when weight loss exceeds an average of 2 lbs (0.9 kg) per week. For subjects with baseline BMI \geq 99th percentile, reduce study drug when weight loss exceeds an average of 2 lbs (0.9 kg)/week.

Dose reduction is implemented through the IWRS, and will be done without breaking the blind. Subjects assigned to the mid-dose may be reduced down to the low-dose and those assigned to the top-dose may be reduced down to the mid-dose, and if necessary, the low-dose in a blinded manner. Dose reduction is not an option for subjects who experience intolerable adverse events related to study medication during the first week of titration (Week 1) during the initial randomization; these subjects will be withdrawn from treatment.

When dose reduction is not appropriate or when dose interruption may be required due to events unrelated to study treatment, subjects may temporarily discontinue from treatment (up to 7 days)

on one or more occasions. Dose interruptions longer than 7 days are possible with agreement from the medical monitor. All subjects undergoing dose interruptions for any duration may be titrated back up to the original dose level based on discretion of the investigator. If study drug has been discontinued for 2 weeks or more, a new titration kit should be ordered through IWRS to resume treatment. Subjects who have a drug holiday following dose reduction due to study medication intolerance will be retitrated to the dose specified for use after dose reduction. For subjects having a drug holiday due to events unrelated to treatment, attempts should be made to retitrated to the initial randomized dose. For treatment interruptions of less than 2 weeks, subjects may resume treatment by dosing every other day for the first week that treatment is resumed.

If symptoms remain intolerable after dose reduction and drug holidays, subjects may be discontinued from treatment. Subjects discontinued from treatment will be encouraged to remain in the trial off-treatment and to continue to make study visits at the regularly scheduled intervals. The last date on which the subject is dosed with study medication should be recorded on the case report form (CRF).

If the subject remains in the trial off-treatment, all study procedures should be continued for the duration of subject participation and they should be encouraged to return at the 56- week time point for measurements and evaluations. For those who choose to completely withdraw from the study at any point, the end of study (Week 56) procedures should be completed.

8.4.5 Discontinuing Study Drug

Abrupt withdrawal of topiramate, a component of VI-0521, has been associated with seizures in individuals without a history of seizures or epilepsy. Subjects discontinuing VI-0521 should be gradually tapered by taking a dose every other day for 1 week prior to stopping treatment altogether.

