9.1.4 Treatment Week 56, End of Study; Early Termination (Visit 16)

The end of study visit will be performed for subjects completing the study or for subjects who are withdrawn from the study prior to completion of the study at the time of their treatment termination. For subjects who withdraw from the study prior to completion, the site will also attempt to contact the subject at or about the 56-week time point to obtain end of study assessments.

Activities at the end of study visit include:

- Administer PHQ-9, C-SSRS, and IWQOL-Kids questionnaires;
- Administer neurocognitive battery (CANTAB);
- Obtain vital signs;
- Obtain weight and waist circumference measurements;
- Measure height and calculate BMI;
- Collect study drug from previous visit, assess treatment compliance, and perform drug accountability;
- Obtain blood sample for chemistry, hematology, and lipids, panel;
- Obtain blood sample for HbA1c;
- Obtain urine sample for routine urinalysis and urine pregnancy test (female only);
- Administer glucose load for OGTT and obtain blood sample for glucose and insulin at 2 hours following oral glucose load (Section 10.10);
- Perform complete physical examination (include Tanner Staging);
- Perform and evaluate 12-lead electrocardiogram (ECG);
- Conduct hand and wrist X-ray;
- Conduct DXA measurement (if applicable);
- Record any changes in concomitant medications;
- Record any adverse events reported or observed;
- Discontinue subject's study participation.

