11.1.4 Mood or Depression Related Events

All subjects will be screened for the presence and severity of depression at screening using a validated survey instrument (PHQ-9) designed for assessment of depression in a primary care setting. The PHQ-9 is a self-administered, nine-item depression module based directly on the diagnostic criteria for major depressive disorder in DSM-V-TR. This questionnaire may be used at the investigator's discretion at other times during the study to aid in diagnosis and evaluation of reported or suspected events of depression.

Suicidality will also be assessed at each study visit using the C-SSRS (see [Appendix 5](#)). The C-SSRS may also be used at the investigator's discretion at unscheduled visits during the study to aid in evaluation and diagnosis of reported or suspected events of suicidality. Should this additional assessment indicate the presence any suicidal behavior, or suicidal ideation with any intent to act on it, study treatment will be stopped, and the investigator must provide appropriate referral to a mental health professional for additional assessment and management. Any such event must be reported to the Medical Monitor and to the sponsor within 24 hours. Subjects must be followed until resolution of these events.

Any mood- or depression-related adverse events must be documented using standard diagnostic criteria and terminology.

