11.4.3 Pregnancy

If any study subject becomes or is found to be pregnant while receiving the investigational product, the investigator must immediately discontinue study treatment and report the pregnancy to VIVUS or designee within 1 business day of learning of the pregnancy.

The investigator will follow the pregnancy until completion or until pregnancy termination (i.e., elective pregnancy termination) and then notify VIVUS or designee of the outcome. The investigator will provide this information as a follow-up to the initial pregnancy report.

For reported pregnancies that result in a live birth, the status of the newborn should be assessed at the time of birth. The status of an aborted fetus should be assessed by gross visual inspection, unless pre-abortion test findings are suggestive of a congenital anomaly.

If pregnancy outcomes meet the criteria for classification as SAEs (i.e., stillbirth, neonatal death, or congenital anomaly), the investigator should follow the procedures for reporting SAEs.

Similarly, any pregnancy outcomes that are considered to be adverse events should be reported as such on the appropriate CRF. However, pregnancy in itself need not be reported as an adverse event if there is no associated adverse outcome.

For reporting purposes, ectopic pregnancies should be reported as SAEs, but because the fetus is not potentially viable, they need not be reported as a pregnancy.

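### Protocol 8.4.5 asks for a one-week taper because of seizure risk, but no visit schedule assigns it to completers, and the dosing, Week 56 and pregnancy sections conflict with it

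*Protocol*

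**What the plan says.** **The taper.** Protocol 8.4.5 gives its reason: "Abrupt withdrawal of topiramate, a component of VI-0521, has been associated with seizures in individuals without a history of seizures or epilepsy". It then says: "Subjects discontinuing VI-0521 should be gradually tapered by taking a dose every other day for 1 week prior to stopping treatment altogether".

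**The dosing period.** Protocol 8.1 states: "Eligible subjects will receive 56 weeks of treatment with either VI-0521, or matching placebo for daily use". Protocol 8.4.3 adds: "Subjects will be instructed to take 1 capsule of study drug every morning with or without food, and with water". Section 9.2 asks sites to keep to the visit windows so that treatment of completers lasts 56 weeks.

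**The last visit.** The Visit 16 list in 9.1.4 includes "Collect study drug from previous visit, assess treatment compliance, and perform drug accountability". It lists no dispensing and no taper instruction, and its last item closes the subject's participation. The same visit is used for subjects withdrawn early and is held when their treatment ends. Section 8.4.3 has subjects hand back all study drug at each visit.

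**Other stops.**
- Section 11.4.3, on pregnancy: "the investigator must immediately discontinue study treatment and report the pregnancy".
- Section 11.1.4, on suicidal behavior or intent: "study treatment will be stopped".
- Section 8.4.4, on intolerance in the first week: "these subjects will be withdrawn from treatment".

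None of these three refers to 8.4.5.

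**The concern.** The protocol identifies a withdrawal hazard and gives an instruction to reduce it, but never puts that instruction into the schedule that sites work from. The subjects most plainly affected are completers on active drug, because every one of them stops at a known time and the visit list for that time makes no mention of a taper.

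A site that follows the dosing and visit sections produces the abrupt stop that 8.4.5 warns about. A site that follows 8.4.5 must depart either from daily dosing before Visit 16 or from drug return after it. Because treatment is blinded, sites meet the question in all three arms and may answer it differently. Early withdrawals meet it too, since drug is collected at the visit held when treatment ends.

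**Working it through.** There is no stated figure to reproduce. The check compares the sections on dosing, dispensing, drug return and stopping, with some day and capsule arithmetic.

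**1. Is the taper mentioned elsewhere?** No other section of the protocol or SAP schedules it or refers to 8.4.5. Section 8.4.4 uses alternate-day dosing for one week, but for resuming treatment after an interruption, not for stopping. The Week 4 to Week 52 list in 9.1.3 has no taper instruction at Week 52, the last scheduled contact before Visit 16.

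**2. Taper before Visit 16.**
- Daily dosing for 56 weeks: 56 × 7 = 392 capsules, which fills the whole period up to a Day 392 visit.
- Alternate-day dosing over 7 days uses 3 or 4 capsules instead of 7.
- Last interval: (21 + 3)/28 = 85.7%, or (21 + 4)/28 = 89.3%.
- Whole study: (385 + 3)/392 = 98.98%, or (385 + 4)/392 = 99.23%.

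Both pairs lie inside the 20% compliance margin of protocol 8.4.6, so a pre-visit taper would not be flagged as non-compliance. It would still replace the daily dosing described in 8.1 and 8.4.3 during the final week, and no section tells the site to do this.

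**3. Taper after Visit 16.**
- It would run to Day 392 + 7 = Day 399, after participation has closed.
- Bottles hold 35 capsules (8.4.1). If the last interval is 21, 28 or 35 days, then 35 − 21 = 14, 35 − 28 = 7 or 35 − 35 = 0 capsules remain.
- Whatever remains is collected at the visit under 9.1.4.

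**4. The other stops.**

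| Section | Speed of stop | Relation to 8.4.5 |
|---|---|---|
| 11.4.3 pregnancy | immediate | direct conflict with a week of further dosing |
| 11.1.4 suicidality | not stated | silent on the taper |
| 8.4.4 Week 1 intolerance | not stated | silent on the taper |

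**5. How many subjects.** The active arms are planned at 50 + 100 = 150 (protocol 6.0). With no dropout and everyone on drug to Week 56, 150 completers on active drug are affected. With the 30% dropout of protocol 12.2 spread evenly, 0.7 × 150 = 105 (35 mid-dose, 70 top-dose). The second figure also assumes that every retained subject is still taking drug.

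**The case against.** The best reply is that 8.4.5 is a general rule on discontinuing drug and need not be repeated at every stop. It says should, not must. It places the taper before the final stop, so a site could fit it into the last week before Visit 16. Supply would allow that, and so would the compliance limits. This stands in part: the taper has no assigned place, but a place is not impossible. It does not remove the conflict, because 8.1 and 8.4.3 prescribe daily dosing for those same days and no visit list tells a site to depart from it.

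Appendix 1 might seem to help, since its dispensing row appears to extend to the Week 56/early termination column. In the text available for this review the columns of that table do not line up: the HbA1c and CANTAB marks fall at visits other than those named in 9.1.3. The entry therefore cannot be relied on. If it is real, it conflicts with 9.1.4.

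Three stronger readings are tempting, and the documents do not support them:

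- **That the other sections all stop drug at once.** Only 11.4.3 does. Sections 11.1.4 and 8.4.4 give no speed and can be read together with 8.4.5. All three concern early stops and are no evidence about completers.
- **That the primary endpoint depends on this.** A pre-visit taper omits 3 or 4 of 392 capsules (0.8% to 1.0%). SAP 6.6.1 already uses Week 56 measurements from subjects who are off drug altogether. The effect on BMI is unquantified and probably small.
- **That 70% of those randomized is the number reaching Visit 16 on drug.** Visit 16 is also the early termination visit, and subjects who have stopped drug are encouraged to attend Week 56.

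**Conclusion.** The point holds as a conflict between sections of the protocol. Followed literally, 8.1, 8.4.3, 9.2 and 9.1.4 give completers the abrupt stop that 8.4.5 warns against. Section 11.4.3 conflicts with 8.4.5 outright, and 11.1.4 and 8.4.4 leave its application open. This is more than missing detail, because obeying the stated schedule defeats the protocol's own safety instruction.

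The size is up to 150 subjects randomized to active drug, or about 105 if dropout is 30%, even across arms, and all retained subjects are still on drug. The documents do not say how many will be on drug at Week 56. The case rests on the safety instruction and on consistency between sites, and not on any demonstrated effect on the Week 56 BMI comparison. It should be corrected. Which clinical rule is right is for the sponsor to settle.

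**What to change.** Reconcile protocol 8.1, 8.4.3, 8.4.5, 9.1.4, 9.2 and 11.4.3, and clarify 8.4.4 and 11.1.4. For each kind of stop (completion, early withdrawal, pregnancy, suicidality, Week 1 intolerance), state whether 8.4.5 applies. For completers, state where it falls relative to drug collection at Visit 16 and to the Week 56 measurement, so that all sites do the same. Carry the answer into the visit lists in 9.1.3 and 9.1.4, and check that the dispensing row of Appendix 1 agrees.

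State also which date counts as the last dose when a taper is used, since SAP 6.7.6 counts treatment-emergent events up to 28 days after it.

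The cost is protocol wording and possibly a change to drug handling at the last visits. No analysis or sample size changes.
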